12.5. Safety Assessments

The following safety assessments will be conducted at the times specified after the beginning of study drug administration:

- Neurological assessment at baseline (prior to study drug administration); 15 minutes, 30 minutes, 1, 2, 4, 8, 12, 18, 24, 30, 36, 42, 48, 54, 60, 66, 72, 84, and 96 hours; and on Day 10 (see [Appendix 4](#)).
- Cardiac assessment (i.e., 12-lead ECG) at baseline (prior to study drug administration); 15 minutes, 30 minutes, 1, 2, 4, 8, 12, 18, 24, 30, 36, 42, 48, 54, 60, 66, 72, 84, and 96 hours; and on Day 10.
- Vital signs (resting heart rate and blood pressure) at baseline (approximately 1 hour prior to surgery), and 1, 2, 4, and 96 hours (i.e., prior to discharge).
- Adverse events from the time the ICF is signed through Day 30.

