9.2. Discussion of Study Design

EXPAREL is approved for infiltration into a surgical site. This multicenter, randomized, double-blind, placebo-controlled study is designed to evaluate the safety, efficacy, and pharmacokinetics of local administration of EXPAREL for prolonged postsurgical analgesia in subjects undergoing third molar extraction. The double blind study design is intended to avoid potential bias resulting from subject or Investigator knowledge of the assigned treatment.

Third molar extraction is a frequently performed surgical procedure that causes considerable postsurgical pain, particularly following removal of impacted lower mandibular third molars. Standard postoperative analgesia following third molar extraction often includes combination opioid analgesics. In this study, all subjects will receive PO oxycodone, as needed, to control breakthrough postsurgical pain.

Neurological and cardiac assessments will be conducted to rule out bupivacaine toxicity related to high plasma exposure.

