13.5. Procedures After Surgery Through 96 Hours

- Collect scheduled blood samples for PK analysis at 15 minutes, 30 minutes, 1, 2, 4, 8, 12, 18, 24, 30, 36, 42, 48, 54, 60, 66, 72, 84, and 96 hours.
- Administer rescue medication (PO oxycodone 5-10 mg) upon request for breakthrough pain, as needed (maximum of every 4 hours).
- Record date, time, and amount of all opioid rescue medication administered.
- Record subject's assessment of pain intensity using the NRS at the following timepoints: 15 minutes, 30 minutes, 1, 2, 4, 6, 8, 12, 24, 48, 72, and 96 hours, and immediately prior to each administration of rescue pain medication, if applicable (see [Appendix 1](#)).
- Perform neurological assessment at 15 minutes, 30 minutes, 1, 2, 4, 8, 12, 18, 24, 30, 36, 42, 48, 54, 60, 66, 72, 84, and 96 hours (see [Appendix 4](#)).
- Conduct 12-lead ECG at 15 minutes, 30 minutes, 1, 2, 4, 8, 12, 18, 24, 30, 36, 42, 48, 54, 60, 66, 72, 84, and 96 hours.
- Measure vital signs (heart rate and blood pressure) after subject has rested in a supine position at 1, 2, 4, and 96 hours (i.e., prior to discharge).
- Obtain overall rating of subject satisfaction with postsurgical pain control using the Likert scale at 24, 48, 72, and 96 hours (see [Appendix 2](#)).
- Have subject complete the PoSSe scale questionnaire at 72 hours (see [Appendix 3](#)).
- Record concomitant medications.
- Record AEs and any treatment(s) for the events.
- If a cardiac event (e.g., myocardial depression, decreased cardiac output, heart block, hypotension, bradycardia, ventricular arrhythmia, or cardiac arrest) or neurological event (e.g., persistent anesthesia, paresthesia, weakness, or paralysis) occurs during the study, an unscheduled PK blood sample should be obtained and, for cardiac events, an ECG should be conducted within 2 hours of the time that the event is noted. If there is a scheduled PK blood draw and ECG within 2 hours before or after the event, an additional PK blood draw and ECG are not needed.
- Discharge subject after the 96-hour assessments have been completed.

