7.7. Safety Analyses

Safety assessments in this study consist of neurological, ECGs, vital signs and AEs. Vital signs will be collected at screening, baseline (prior to surgery) and 1, 2, 4 and 96 hours after surgery. Adverse events will be collected from the time of informed consent through Day 30.

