7.9. Interim Analysis

7.9.1. Pharmacokinetic Review

After the first 30 subjects have completed the study through Day 10, the plasma samples from the subjects who received EXPAREL will be reviewed by an unblinded pharmacokineticist not involved in the conduct of the study to determine the median time to the observed maximum plasma concentration. The pharmacokineticist will make a recommendation on the PK sampling

times so that subsequent assessment and endpoints are collected through the median time to maximum plasma concentration (T_{max}) plus at least 24 hours. This recommendation may indicate additional, fewer or no change to the PK sample times. The study team may, based on the pharmacokineticists findings, decide to amend the protocol.

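### No blood pressure reading is scheduled between 4 h and 96 h, so if median Tmax falls in that interval the vital-sign endpoint could miss unrecognised change at peak exposure

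*Protocol*

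**What the plan says.** **Vital signs.** Protocol 12.5 sets heart rate and blood pressure at "baseline (approximately 1 hour prior to surgery), and 1, 2, 4, and 96 hours (i.e., prior to discharge". The Synopsis, Table 1 and 13.5 agree, and SAP 7.7 says: "Vital signs will be collected at screening, baseline (prior to surgery) and 1, 2, 4 and 96 hours after surgery".

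**ECG, PK and neurological assessment.** Protocol 13.5 reads "Conduct 12-lead ECG at 15 minutes, 30 minutes, 1, 2, 4, 8, 12, 18, 24, 30, 36, 42, 48, 54, 60, 66, 72, 84", and the list ends with 96 h. PK samples (12.3) and neurological assessments (12.5) fall at the same hours. Under 13.1 subjects are in the facility for the full 96 h. Sections 13.1.3 and 13.1.4 place the subject supine for vital signs and ECG alike.

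**Cardiac events.** Hypotension is the fourth of seven examples of a cardiac event in 9.1 and 13.5. When such an event occurs, "an unscheduled PK blood sample should be obtained and, for cardiac events, an ECG should be conducted within 2 hours" of its being noted.

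**Endpoints and reporting.** Protocol 12.6 ties the ECG endpoint to the time nearest the median Tmax, and SAP 7.7.2 highlights that time. The vital-sign endpoint is change from baseline at its own scheduled times, and SAP 7.7.3 has no link to Tmax. SAP Table 5 sets low criteria of 90 mmHg or less (systolic) and 50 mmHg or less (diastolic). These feed Table 14.3-3.2, which SAP section 5 names as a topline table. Its shells show baseline, 1, 2 and 4 h. The programmer note to Table 14.3-3.1 names the same times, and Listing 16.2-15 also ends at 4 h.

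**Tmax.** Neither document gives a value. SAP 7.9.1 derives the median from the first 30 subjects.

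**The concern.** The study drug releases bupivacaine slowly (Protocol 7.3), so exposure after 4 h is of interest. That is presumably why ECG, PK and neurological checks are so dense through 84 h. Blood pressure is the one planned safety measure that leaves this period out. An ECG does not measure it, and the neurological questions (orientation, numbness, taste, hearing, vision, twitching) do not ask about it.

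The event-triggered sampling rule does not close the gap, because it starts only when an event has been noted. Between 4 h and 96 h nothing on the schedule would reveal a fall in blood pressure that caused no symptoms.

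What is at stake is how a clean table of abnormal vital signs can be read. As the shells stand, the topline blood pressure evidence covers the first 4 h only. Absence of low values there says nothing about the following days, yet a reader could take it as reassurance for the whole stay.

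**Working it through.** The plan states no figure of its own on this point. The check is a count of two schedules and a distance.

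**1. Visits in the interval.** ECG times strictly between 4 h and 96 h (Protocol 12.5, 13.5): 8, 12, 18, 24, 30, 36, 42, 48, 54, 60, 66, 72 and 84 h. That is 13. Scheduled blood pressure readings in the same interval: 0.

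**2. Length of the interval.** 96 − 4 = 92 h, or 92/96 = 95.8% of the in-house stay. With visit windows of ±15 min at 4 h and ±4 h at 96 h, it runs from 92 − 4.25 = 87.75 h to 100 − 3.75 = 96.25 h. The percentage describes the spacing of readings. It should not be read as lost coverage, since spot readings cover few hours under any schedule.

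**3. Pairing.** There are 19 post-dose ECG/PK times through 96 h. Blood pressure is paired with 4 of them (1, 2, 4 and 96 h) and not with 19 − 4 = 15, namely the 13 above plus 0.25 and 0.5 h.

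**4. Distance from a possible median Tmax (T) to the nearest scheduled reading.** For T between 4 and 96 h, distance = min(T − 4, 96 − T). For earlier T, it is the distance to the nearest of 1, 2 and 4 h. All values of T are assumptions.

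| Assumed T (h) | Nearest reading (h) | Distance (h) |
|---|---|---|
| 0.25 | 1 | 0.75 |
| 0.5 | 1 | 0.5 |
| 1, 2 or 4 | same time | 0 |
| 8 | 4 | 4 |
| 12 | 4 | 8 |
| 24 | 4 | 20 |
| 48 | 4 | 44 |
| 72 | 96 | 24 |

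A median between two sampling times up to 4 h, such as 3 h, would be at most 1 h from a reading (3 − 2 = 4 − 3 = 1). The result therefore turns on which side of 4 h the median falls, and by how much.

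**5. Shells against collection.** Four post-dose readings are collected (1, 2, 4 and 96 h). The vital-sign table and listing shells provide for three. The only reading after 4 h would not be displayed.

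**The case against.** The schedule is a deliberate choice, stated consistently in the protocol text and in SAP 7.7, and several stronger readings of it fail.

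- **Stated purpose.** Protocol 9.2 says "Neurological and cardiac assessments will be conducted to rule out bupivacaine toxicity related to high plasma exposure". A reader might infer that sparse blood pressure contradicts this. It does not: 12.5 defines the cardiac assessment as the 12-lead ECG and lists vital signs separately.
- **SAP 7.9.1.** It speaks of timing such that "subsequent assessment and endpoints are collected through the median time to maximum plasma concentration" plus at least 24 h. A reader might infer that the blood pressure schedule breaches this. But the recommendation concerns PK sampling times, and the 96 h reading lies at or beyond Tmax plus 24 h for any median up to 72 h (72 + 24 = 96).
- **Late peak.** The SAP addendum lists a late Cmax and Tmax (after 2 h), which might suggest that a late peak is expected. The same note lists an early pair (0 to 2 h). A maximum within a window does not show when the overall peak occurs, and the late window includes the 4 h reading.
- **Other detection.** Heart rate is summarised at every ECG time (SAP 7.7.2). Adverse events are recorded throughout, so recognised hypotension would be counted. Blood pressure could also be taken for clinical reasons or at the final evaluation after withdrawal (10.3.2).
- **Prior record.** Protocol 7.4 reports no cardiovascular signal at doses up to 665 mg, and this study uses 133 mg.

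These points stand, and they narrow the concern to scheduled blood pressure and unrecognised change. They do not remove it. The prior record lowers the expected yield but cannot supply this trial's data. The amendment allowed after the PK review might change timepoints, but no text commits to adding blood pressure.

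**Conclusion.** The concern holds in a limited, conditional form. The counts (0 readings, 13 visits, 92 h) are certain. The consequence depends on Tmax, which the documents do not give. With a median of 4 h or earlier, the planned readings are adequate. With a median well after 4 h, the blood pressure part of the vital-sign endpoint would be observed 8 to 44 h from the peak over the assumed range of 12 to 48 h, and could miss asymptomatic change there.

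A reader might go further and conclude that the trial is blind to cardiovascular toxicity, or that an effect at peak exposure will be missed. The documents support neither, given the dense ECGs, the adverse event recording and the unknown Tmax. The efficacy analyses are unaffected. The omission of the 96 h reading from the shells is a separate, unconditional inconsistency with SAP 7.7.

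**What to change.** - **Protocol Table 1, 12.5 and 13.5:** pair a blood pressure reading with the existing supine ECG visits between 4 h and 96 h.
- **SAP 7.7.3:** also report the vital-sign change at the visit closest to median Tmax, as is already done for ECG.
- **SAP shells:** add the 96 h reading to Tables 14.3-3.1 and 14.3-3.2 and to Listing 16.2-15, along with any readings newly scheduled.
- **If the schedule cannot be changed:** state in the study report that scheduled blood pressure data do not address the period between 4 h and 96 h. The SAP and shell changes can still be made.

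The cost is a short protocol amendment and up to 13 readings per subject, or 13 × 175 = 2,275 if all planned subjects had every one. Subjects are already in-house and supine for the ECG, so no new visit is needed. The downside is slightly longer visits, some of them at night. No change to the response to cardiac events is proposed.

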12.6. Safety Endpoints

The following safety endpoints will be assessed based on the safety measurements conducted at the specified timepoints:

- Summary of neurological assessments (proportion of subjects who are oriented, and proportion of subjects who have any of the neurological events).
- Change from baseline in ECG data closest to the median T_{max} .
- Change from baseline in vital signs (resting heart rate and blood pressure) at each assessed timepoint.
- Incidence of treatment-emergent AEs (TEAEs) through Day 30.

12.7. Appropriateness of Measures

Endpoints selected for this study were based on validated methodologies and other well established clinical measurements used in peer-reviewed studies in both the peer reviewed literature and at regulatory authorities.

The neurological and cardiac safety assessments are based on the known signs and symptoms associated with systemic bupivacaine toxicity.

13. STUDY PROCEDURES

A time and events schedule for all study procedures is provided in [Table 1](#).

13.1. Instructions for Conducting Procedures and Measures

All safety, efficacy, and PK assessments conducted after baseline will be timed from the *beginning of study drug administration*.

At timepoints when multiple assessments coincide, the NRS pain intensity assessments will be conducted first, if applicable.

Day 1 is defined as the day on which study drug is administered. The beginning of surgery is defined as the time of the first incision. The end of surgery is defined as the time of the last suture. Postsurgical is defined as after the end of surgery.

Subjects will remain in the research facility for 96 hours after study drug administration; therefore, postsurgical analgesia and collection of study data through the primary endpoint will take place under the supervision of study staff.

13.1.1. Pain Intensity Assessments

Pain intensity will be assessed using the NRS (see [Appendix 1](#)). To assess pain intensity, the subject will assume a resting position that does not exacerbate his or her postsurgical pain. The subject will rest in this position for at least 5 minutes before responding to the following question, *“On a scale of 0 to 10, where 0 = no pain and 10 = worst possible pain, how much pain are you having right now?”* The subject’s response will be recorded.

13.1.2. Neurological Assessment

The neurological assessment will include the subject’s orientation. Additionally, the subject will be asked whether he or she is experiencing any numbness of the lips, the tongue, or around the mouth; a metallic taste in the mouth; problems with hearing; problems with vision; or muscles twitching (see [Appendix 4](#)).

13.1.3. Vital Signs

Vital signs (heart rate and blood pressure) will be measured after the subject has rested in a supine position. The subject will remain in a supine position during the assessment.

13.1.4. Electrocardiogram

The 12-lead ECGs will be conducted after the subject has rested in a supine position for 5 minutes.

13.1.5. Subject Satisfaction with Postsurgical Pain Control

The subject’s satisfaction with postsurgical pain control will be assessed using the Likert Scale at 24, 48, 72, and 96 hours, and on Day 10 (see [Appendix 2](#)).

13.1.6. Postoperative Symptom Severity (PoSSe) Scale Questionnaire

The PoSSe scale questionnaire will be completed at 72 hours and on Day 7 (see [Appendix 3](#)).

13.2. Screening Procedures

- Explain study purpose and procedures.
- Obtain signed ICF.
- Assess eligibility.
- Record relevant medical/surgical history, demographics, and baseline characteristics.
- Record concomitant medications.
- Perform dental examination.
- Perform physical examination including height and weight.
- Measure vital signs (heart rate and blood pressure) after subject has rested in a supine position.
- Conduct 12-lead ECG.
- Perform urine pregnancy test for women of childbearing potential.
- Perform urine drug screen.
- Record AEs starting at signing of the ICF.

13.3. Baseline Procedures (Day 1)

- Confirm eligibility.
- Update relevant medical history.
- Perform urine pregnancy test for women of childbearing potential before study drug administration.
- Perform urine drug screen.
- Measure vital signs (heart rate and blood pressure) after subject has rested in a supine position.
- Perform neurological assessment (see [Appendix 4](#)).
- Conduct 12-lead ECG.
- Collect baseline (pre-dose) blood sample for PK analysis prior to study drug administration.
- Record changes to concomitant medications since screening.
- Record AEs.
- Randomize subject and prepare study drug.

13.4. Intraoperative Procedures (Day 1)

- Administer dental nerve block with lidocaine 2% with epinephrine 1:100,000.
- Perform bilateral third molar extraction under local anesthesia.
- At the end of surgery, administer study drug according to the randomization schedule.
- Record start and stop time of study drug administration.
- Record start and stop times of surgery.
- Record concomitant medications.
- Record AEs and any treatment(s) for the events.

13.5. Procedures After Surgery Through 96 Hours

- Collect scheduled blood samples for PK analysis at 15 minutes, 30 minutes, 1, 2, 4, 8, 12, 18, 24, 30, 36, 42, 48, 54, 60, 66, 72, 84, and 96 hours.
- Administer rescue medication (PO oxycodone 5-10 mg) upon request for breakthrough pain, as needed (maximum of every 4 hours).
- Record date, time, and amount of all opioid rescue medication administered.
- Record subject's assessment of pain intensity using the NRS at the following timepoints: 15 minutes, 30 minutes, 1, 2, 4, 6, 8, 12, 24, 48, 72, and 96 hours, and immediately prior to each administration of rescue pain medication, if applicable (see [Appendix 1](#)).
- Perform neurological assessment at 15 minutes, 30 minutes, 1, 2, 4, 8, 12, 18, 24, 30, 36, 42, 48, 54, 60, 66, 72, 84, and 96 hours (see [Appendix 4](#)).
- Conduct 12-lead ECG at 15 minutes, 30 minutes, 1, 2, 4, 8, 12, 18, 24, 30, 36, 42, 48, 54, 60, 66, 72, 84, and 96 hours.
- Measure vital signs (heart rate and blood pressure) after subject has rested in a supine position at 1, 2, 4, and 96 hours (i.e., prior to discharge).
- Obtain overall rating of subject satisfaction with postsurgical pain control using the Likert scale at 24, 48, 72, and 96 hours (see [Appendix 2](#)).
- Have subject complete the PoSSe scale questionnaire at 72 hours (see [Appendix 3](#)).
- Record concomitant medications.
- Record AEs and any treatment(s) for the events.
- If a cardiac event (e.g., myocardial depression, decreased cardiac output, heart block, hypotension, bradycardia, ventricular arrhythmia, or cardiac arrest) or neurological event (e.g., persistent anesthesia, paresthesia, weakness, or paralysis) occurs during the study, an unscheduled PK blood sample should be obtained and, for cardiac events, an ECG should be conducted within 2 hours of the time that the event is noted. If there is a scheduled PK blood draw and ECG within 2 hours before or after the event, an additional PK blood draw and ECG are not needed.
- Discharge subject after the 96-hour assessments have been completed.

13.6. Day 7 Visit

- Collect scheduled blood sample for PK analysis.
- Document any unscheduled phone calls or office visits related to pain after hospital discharge.
- Have subject complete the PoSSe scale questionnaire (see [Appendix 3](#)).
- Record concomitant medications including opioid rescue.
- Record AEs and any treatment(s) for the events.

13.7. Day 10 Visit

- Collect scheduled blood sample for PK analysis.
- Perform neurological assessment (see [Appendix 4](#)).
- Conduct 12-lead ECG.
- Document any unscheduled phone calls or office visits related to pain since Day 7.
- Obtain overall rating of subject satisfaction with postsurgical pain control using the Likert scale (see [Appendix 2](#)).
- Record concomitant medications including opioid rescue.
- Record AEs and any treatment(s) for the events.

13.8. Day 30 Phone Call

- Document any unscheduled phone calls or office visits related to pain since Day 10.
- Record concomitant medications.
- Record AEs and any treatment(s) for the events.

14. ADVERSE EVENT REPORTING

Consistent with the current regulatory guidance provided by the US CFR and the ICH GCP, AEs and SAEs are defined in [Section 14.1.1](#) and [Section 14.2.1](#), respectively.

The concepts of AEs and SAEs represent regulatory instruments used to evaluate and monitor the safety of clinical study subjects. Therefore, these terms only apply in light of their regulatory definition. The term serious, in a regulatory sense, does not necessarily mean severe. The SAE concept is used primarily to identify, during the conduct of the study, those SAEs that may require expedited reporting to regulatory authorities.

14.1. Adverse Events

14.1.1. Definitions

Definition of Adverse Event (AE): Any untoward medical occurrence associated with the use of a drug in humans, whether or not considered drug related. An AE (also referred to as an adverse experience) can be any unfavorable and unintended sign (e.g., abnormal laboratory finding), symptom, or disease temporally associated with the use of a drug, without any judgment about causality. An AE can arise from any use of the drug (e.g., off-label use in combination with another drug) and from any route of administration, formulation, or dose, including an overdose.

An AE can be any unfavorable and unintended change in a body structure or body function. Adverse events include any clinically significant deterioration of a subject's medical status. The AE may involve any organ or system and can be represented by the new onset or deterioration of a disease, a syndrome, a symptom, a physical sign, as well as by findings and results of instrumental examinations and laboratory tests. Any medically relevant and untoward change after the subject signs the ICF, including frequency or pattern changes for a fluctuating condition (e.g., migraine) is considered an AE.

An AE that occurs after the ICF is signed and before the start of the study drug administration is identified as a pretreatment AE (PTAE). An AE that occurs after the administration of the study treatment is considered a TEAE.

Definition of Adverse Reaction: Any AE caused by a drug. Adverse reactions are a subset of all suspected adverse reactions for which there is reason to conclude that the drug caused the event.

Definition of Suspected Adverse Reaction: Any AE for which there is a reasonable possibility that the drug caused the AE. For the purposes of IND safety reporting, 'reasonable possibility' means there is evidence to suggest a causal relationship between the drug and the AE.

A suspected adverse reaction implies a lesser degree of certainty about causality than adverse reaction, which means any AE caused by a drug. Suspected adverse reactions are a subset of all AEs for which there is a reasonable possibility that the drug caused the event.

